### **13.8 Analysis of Exploratory Endpoints**

Biomarkers of blood and tissue: Analyses of blood, imaging, and tissue biomarkers will be based on descriptive statistics, as appropriate for the biomarker.

To examine response according to pre-treatment levels of biomarkers, the study sample will be divided retrospectively according to the primary endpoint of response or non-response. Pre-treatment biomarker levels will be summarized descriptively for the two response groups and compared using Wilcoxon rank-sum tests for markers measured on a continuous scale, or Fisher's exact tests for those measured on a categorical scale. Where appropriate, visualization of the relationship between baseline marker levels and the distributions of PFS or OS will employ Kaplan-Meier estimates stratified by biomarker levels. Medians of the time-to-event endpoints will be shown with two-sided 90% confidence intervals; the distributions of PFS and OS will be compared across biomarker strata using the log-rank test.

Changes in biomarkers between pretreatment and progression or treatment discontinuation will be calculated (post-pre) for each patient and summarized descriptively. In addition, the correlation of changes in tissue biomarkers with changes in measures of peripheral blood markers will be explored graphically, or by appropriate statistical methods based on data availability, to assess associations.

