### 1.3 Secondary Objectives

1. To determine the toxicity of pembrolizumab in patients with recurrent high-grade meningioma (WHO grade II atypical meningioma and WHO grade III anaplastic meningioma)
2. To estimate the overall survival of patients with recurrent high-grade meningioma receiving pembrolizumab
3. To estimate the response rate of patients with recurrent high grade meningioma receiving pembrolizumab

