## 2. BACKGROUND

### 2.1 Meningioma

Meningiomas are the most common primary brain tumor, with a prevalence of 170,000 cases in the US and an annual incidence of 18,000 new cases. Most meningiomas are of the typical variety – World Health Organization (WHO) grade I. However, depending on their location within the nervous system, grade I meningiomas can cause significant morbidity or mortality. Even after surgical resection, recurrence rates can be as high as 20%, and patients with grade I tumors have reduced long-term survival.

Approximately 20% of meningiomas are atypical (WHO grade II) and anaplastic (WHO grade III), defined by increased mitoses, necrosis, higher nuclear to cytoplasmic ratios, or histologic appearance resembling carcinoma, sarcoma, or melanoma. Recurrence rates for WHO grade II and III meningiomas are 40% and 80%, respectively. The prognosis of atypical and anaplastic meningiomas is poor, with 5-year overall survival rates between 47-65%.

Treatment options, particularly for the atypical or anaplastic meningiomas, are limited. Radiation is frequently used as an adjunct to surgery; however, there are no effective chemotherapeutic options when surgery and radiation fail to offer durable long-term disease

control. Traditional cytotoxic agents have minimal activity in this setting, and targeted agents in unselected patients have demonstrated modest benefit at best. Response rate has been 0% in nearly all studies of systemic therapy in recurrent tumors of all grades. A poor understanding of what drives meningioma development has hampered the development of therapeutic agents to supplement surgery and radiation. Therefore these patients have limited therapeutic options and effective treatments are greatly needed. While genomic studies have revealed mutations in oncogenes such as SMO and AKT in a small subset of meningioma, most tumors do not have mutations that can be targeted. Studies of high grade tumors have failed to reveal obvious drivers of malignant progression, rendering these tumors exceedingly challenging to treat.

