### **9.3.3 RNA-sequencing**

RNA Sequencing from FFPE includes plating, poly-A selection and cDNA synthesis, library preparation, sequencing, sample identification QC, and data storage. RNA will be extracted from tissue sections and RNA libraries will be prepared for sequencing by NEBNext Ultra RNA Library Prep Kit for Illumina (New England BioLabs, Ipswich, MA), including the removal of large and small RNA, synthesis of cDNA, and construction of cDNA libraries. Libraries will be barcoded using NEBNext Multiplex Oligos for Illumina (NEB). Libraries will be sequenced using Illumina HiSeq 2500, with paired-end 100bp reads. We will follow the analytic pipelines as previously described. Paired-end reads will be aligned to UCSC human transcriptome 19 (hg19) using TopHat (Bowtie v2.0.9). Alignment quality and read distribute will be assessed via SAMtools (v0.1.19). Transcript assembly will be conducted using cufflinks (v2.2.1). Normalized expression data will be generated from aligned BAM files using cuffnorm and cuffdiff. Statistically significant genes differentially expressed between responder samples and non-responders will be determined.

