### **9.3.5.3 Statistical Considerations**

Exploratory analyses will be conducted. As data permit, analyses of the MRI parameters will be summarized by descriptive statistics, including mean, median and standard deviation. Differences in these parameters between responders and non-responders will be compared with parametric or nonparametric techniques as permitted by the data. For correlative analyses, Cox proportional hazards model will be used to explore the relationship between parameters measured at baseline and PFS and OS. Logistic regression will be used to explore the relationship between parameters measured at baseline and the binary outcome of alive and progression-free at 6 months (APF6).

Overall, the plan is to determine whether the baseline measurements are prognostic for the entire group. We will determine whether there is an association between the baseline measurements and response adjusting for the patient cohort. A priori we do not think that the association between the baseline measurements and response will depend on the type of mutation and treatment. However, if the association between baseline measurements and response are not found to be statistically significantly associated, we will do subgroup analyses to determine if there might be differences in the association between baseline variables and response among the groups. Specifically, we will do perform the analysis for each group separately. We will also do tests for interaction between the cohort group and the baseline variable, though these will likely not have sufficient power due to the small sample sizes.

The overall plan for determining whether a change in the parameters from baseline is associated with response is to first evaluate the association with the change between baseline and first MRI time point (6 weeks into therapy). An additional analysis will be done that uses all the available MRI assessment time points. To account for multiple MRI time points, we will treat the change in MRI from baseline as a time-dependent variable (which could change at each assessment).

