### **13.2 Endpoints**

#### **Primary Endpoints:**

The primary endpoint is progression-free survival at 6 months (PFS6). PFS6 is defined as not having progressive disease or death within six months of the first day of treatment. Contrast-enhanced cranial magnetic resonance imaging (MRI) will be performed every 6 weeks. Standard response criteria will be used (see [Section 11.0](#)).

All patients meeting the eligibility criteria that have signed the consent form and have begun treatment will be considered evaluable for the analysis of primary endpoint.

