### **13.6 Analysis of Primary Endpoints**

The goal will be to enroll 24 patients. The primary endpoint is the rate of 6 month PFS. The trial will distinguish between 6 month PFS rates of 26% vs. 52%. The historical control of 6 month PFS is based on a recent meta-analysis showing a PFS-6 of 26% in recurrent Grade II/III meningiomas and other studies in this patient population. If at least 10 patients demonstrate 6 month PFS, among the 24 evaluable patients, the agent will be considered worthy of further study, yielding at least 88% power to detect a true 6 month PFS rate of at least 52%, using an exact binomial test with a one-sided significance level of 0.1, against the null hypothesis of 26% 6-month PFS.

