### **13.7 Analysis of Secondary Endpoints**

Safety and Tolerability: All adverse events recorded during the trial will be summarized for all patients having received one or more doses of pembrolizumab. The proportions of patients with grade-3 or higher hematologic toxicities or grade-3 or higher neurologic toxicities will be presented with 90% exact binomial confidence intervals. The incidence of events that are new or worsening from the time of first dose of treatment will be summarized according to system organ class and/or preferred term, severity (based on CTCAE grade), type of adverse event, and relation to study treatment. Deaths reportable as SAEs and non-fatal serious adverse events will be listed by patient and tabulated by primary system organ class, and type of adverse event.

Overall Survival: The distributions of overall survival will be summarized using the method of Kaplan-Meier. The follow-up of patients who are alive at the time of analysis will be censored at the date of last assessment of vital status. Median OS will be presented and accompanied by 90% confidence intervals estimated using log(-log(survival)) methodology. Survival point estimates at 3 and 6 months will also be presented with confidence intervals.

Intracranial/Extracranial Response: Contrast-enhanced cranial magnetic resonance imaging (MRI) will be performed every 6 weeks. The proportion of patients with intracranial response (CR, PR or SD by RANO) will be presented with a two-sided, 90% exact binomial confidence interval.

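### Section 13.8 groups patients for the biomarker tests by a primary endpoint of response, but the primary endpoint is PFS6, so the grouping is undefined and could leave too few responders on one reading

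*Combined protocol and SAP*

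**What the plan says.** Section 13.8 sets up the two groups for the pre-treatment biomarker comparison: "the study sample will be divided retrospectively according to the primary endpoint of response or non-response". Continuous markers are then compared by Wilcoxon rank-sum tests and categorical markers by Fisher's exact tests.

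The endpoint definitions differ from this. Section 13.2 states "The primary endpoint is progression-free survival at 6 months (PFS6"), and Section 13.6 repeats it: "The primary endpoint is the rate of 6 month PFS". Response is a secondary objective in Section 1.3 ("To estimate the response rate of patients with recurrent high grade meningioma receiving pembrolizumab") and a secondary endpoint in Section 13.2.

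Response itself has two meanings. Section 11.3.1.1 defines SD as disease that does not qualify as CR, PR or progression. Section 13.7 counts SD as response: "The proportion of patients with intracranial response (CR, PR or SD by RANO").

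Two other sections use the same kind of split without a definition. Section 9.3.3 says: "Statistically significant genes differentially expressed between responder samples and non-responders will be determined". Section 9.3.5.3, on MRI parameters, says: "Differences in these parameters between responders and non-responders will be compared with parametric or nonparametric techniques as permitted by the data". Section 9.3.5.3 also has a logistic model for being alive without progression at 6 months (APF6), and Cox models for PFS and OS. Section 13.8 also plans log-rank comparisons of PFS and OS across biomarker strata.

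**The concern.** An analysis rule that names a non-existent endpoint cannot be carried out as written. Someone must decide what it means, and because the division is retrospective, that decision could be taken after outcomes and marker values are known. In 24 patients, moving a few from one group to the other can change which markers stand out.

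The possible readings also differ greatly in group size. The background in Section 2.1 reports of earlier treatments: "Response rate has been 0% in nearly all studies of systemic therapy in recurrent tumors of all grades". If responder is taken to mean CR or PR, and pembrolizumab does little better than those agents, one side of the comparison could be empty or hold a single patient. The Wilcoxon, Fisher and differential-expression comparisons would then yield little or nothing, after the tissue has been collected and sequenced.

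**Working it through.** **Inputs.** From Section 13.6: 24 evaluable patients, PFS6 of 26% (null) and 52% (target), success at 10 or more, one-sided level 0.1, power at least 88%. The documents give no CR/PR rate for pembrolizumab, so the CR/PR rates below are assumptions.

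**Step 1: the plan's own figure.** With X binomial on 24 patients:
- Power: P(X ≥ 10 | 0.52) = 0.888.
- Type I error: P(X ≥ 10 | 0.26) = 0.069. A cutoff of 9 would give 0.147, above 0.1.

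The stated design reproduces. The plan states no responder count or power for the biomarker comparison.

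**Step 2: three readings of the split.**
1. *PFS6 status*, if the words primary endpoint govern.
2. *CR/PR*, if the word response governs and Section 11.3.1.1 supplies its meaning.
3. *CR/PR/SD*, if Section 13.7 supplies its meaning.

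**Step 3: group sizes under PFS6.** 24 × 0.26 = 6.24, about 6 versus 18. 24 × 0.52 = 12.48, about 12 versus 12. Even at 26%, the chance of at most one patient in the PFS6-success group is 0.007, and the chance of at least three is 0.968.

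**Step 4: group sizes under CR/PR.** For a true rate p, P(0) = (1 − p)^24 and P(≤ 1) = (1 − p)^24 + 24p(1 − p)^23. At 5%, this is 0.292 + 0.369 = 0.661.

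| Assumed CR/PR rate | Expected responders | P(0) | P(≤ 1) | P(≤ 2) |
|---|---|---|---|---|
| 2% | 0.48 | 0.616 | 0.917 | 0.988 |
| 5% | 1.2 | 0.292 | 0.661 | 0.884 |
| 10% | 2.4 | 0.080 | 0.292 | 0.564 |
| 20% | 4.8 | 0.005 | 0.033 | 0.115 |

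**Step 5: what the tests can show.** With m responders among 24, the smallest two-sided exact Wilcoxon p-value is 2/C(24, m).
- m = 0: no comparison is possible.
- m = 1: 2/24 = 0.083, so 0.05 cannot be reached. Fisher's test can reach 1/24 = 0.042, but only if that one patient alone carries the marker.
- m = 2: 2/276 = 0.007, so significance is possible, but power is low.

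Simulated Wilcoxon power (4,000 runs, normally distributed marker, assumed shift of 1.5 SD, two-sided 0.05) is about 43% with 2 responders, 55% with 3, 82% for 6 versus 18 and 92% for 12 versus 12. The 0.05 level is also an assumption, because Section 13.8 sets none for these tests.

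**Step 6: CR/PR/SD.** No rate is given. A patient progression-free at 6 months would ordinarily have shown at least SD on the scheduled scans, so this group should be roughly as large as the PFS6-success group or larger. The non-responders could then be the small group.

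**The case against.** The strongest defence is that the sentence names the primary endpoint and the trial has only one. Read that way, the groups are those of Step 3, and the word response is a slip. That may well be the intention, and the fix adopts it. It does not settle the text, however: Section 13.7, immediately before, gives response a different meaning, and Section 9.3.3 refers to responders without mentioning the primary endpoint.

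A second objection is that the exploratory objectives in Section 1.4 concern response, so moving everything to PFS6 would change the question. In a single arm, PFS6 status also mixes prognosis with drug effect. This stands, and it is why the fix keeps a CR/PR comparison alongside.

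Third, the objectives do not rest on this split alone. The log-rank, Cox and APF6 analyses need no responder group. This also stands, in part: the APF6 model covers baseline MRI parameters only, no cut-points are given for the biomarker strata, and Section 9.3.3 plans no alternative for RNA-sequencing.

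A reader might infer that the biomarker objective will probably have no usable responder group. The documents do not support that. The 0% in Section 2.1 describes earlier agents across all grades. Section 2.3 hypothesises that PD-L1-expressing tumours will respond to pembrolizumab and gives no rate. The PFS6 and CR/PR/SD readings do not imply an empty responder group, and at a 10% CR/PR rate at most one responder is already the less likely outcome. Nor do the documents say that PFS6 was made the primary endpoint because responses are rare.

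**Conclusion.** Section 13.8 contradicts the endpoint definitions in Sections 13.2 and 13.6, and the groups for the Wilcoxon and Fisher tests are therefore undefined. The same gap affects RNA-sequencing and the responder comparison of MRI parameters. This rests on the text alone.

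The practical risk is conditional. A near-empty responder group becomes likely only if response means CR/PR and the true rate is about 5% or lower. The PFS6 grouping gives workable numbers at both design rates, on the basis of 24 evaluable patients who all have marker data; missing tissue would shrink every group.

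The affected analyses are exploratory, and other planned PFS and OS analyses partly cover the objectives. The primary test and its operating characteristics are unaffected. The correction is still worth making before outcomes are linked to markers, because it removes an avoidable choice made after the data are seen.

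**What to change.** - **Section 13.8:** replace the reference to a primary endpoint of response with the primary endpoint PFS6, the groups being patients alive without progression at 6 months and all others, classified as in the primary analysis.
- **Section 9.3.3:** use the same two groups for differential expression.
- **CR/PR:** keep it as a separately labelled, descriptive response comparison, since Section 1.4 asks about response.
- **Section 9.3.5.3:** keep the APF6 model for baseline MRI parameters and define responder where that section uses the word.
- **Section 13.7:** reconcile the inclusion of SD with Section 11.3.1.1, for example by reporting CR/PR as response and CR/PR/SD under a different name.

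The cost is wording only, with no new patients, samples or assessments. There is one small downside: PFS6 groups in a single arm also reflect prognosis, so findings should be labelled as associations with outcome on treatment, not as predictors of drug effect.

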### **9.3 Methodology**

#### **9.3.1 RNAscope assay and evaluation**

FFPE sections will be hybridized separately with Probe-Hs-PDL1-v2 and a PD-1 specific probe and then visualized. Probe-DapB and Probe-Hs-PPIB will be used as negative and positive controls respectively. Stained slides will be digitally scanned, then visually evaluated by two pathologists. We will use an open-source CellProfiler image analysis software (<http://www.cellprofiler.org/>) to analyze the number of dots per cell using a customized analysis pipeline that we have developed, optimized and tested. ([http://www.cellprofiler.org/published\\_pipelines.shtml](http://www.cellprofiler.org/published_pipelines.shtml)).

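### For blood and tissue markers, section 13.8 tests PFS and OS only by log-rank across undefined strata, although the plan already uses a Cox model on baseline MRI parameters for the same outcomes

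*Combined protocol and SAP*

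**What the plan says.** Section 13.8 (Analysis of Exploratory Endpoints) covers blood, imaging and tissue markers and opens by calling the work descriptive: "Analyses of blood, imaging, and tissue biomarkers will be based on descriptive statistics, as appropriate for the biomarker". It then gives two kinds of comparison.

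- **Marker against response status.** Continuous markers stay on their own scale and are "compared using Wilcoxon rank-sum tests for markers measured on a continuous scale"; categorical markers get Fisher's exact test.
- **Marker against PFS and OS.** Where appropriate, the display "will employ Kaplan-Meier estimates stratified by biomarker levels", and "the distributions of PFS and OS will be compared across biomarker strata using the log-rank test". No cut point, number of strata or rule for choosing them is given.

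Several of the markers are quantitative. Section 9.3.1 uses image software "to analyze the number of dots per cell using a customized analysis pipeline", section 9.3.2 scores immunohistochemistry from digital images, and section 9.3.3 produces normalized RNA-seq expression.

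For MRI parameters, section 9.3.5.3 takes another route to the same outcomes: "Cox proportional hazards model will be used to explore the relationship between parameters measured at baseline and PFS and OS". It mentions no cut. It also says "Logistic regression will be used to explore the relationship between parameters measured at baseline and the binary outcome" of being alive and progression-free at 6 months, and for later scans "we will treat the change in MRI from baseline as a time-dependent variable".

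**The concern.** A continuous blood or tissue marker has to be cut before the log-rank test in 13.8 can be applied. Cutting discards the ordering within each stratum. The Wilcoxon test avoids the cut but reduces the outcome to two groups. So no planned test of a continuous blood or tissue marker uses both the full marker scale and the full follow-up time, and the documents do not say why these markers are handled differently from MRI parameters.

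Two things are at stake. With about 24 patients, a moderate association is already hard to detect and a split makes it harder. And because the cut is open, it could be settled after outcomes are known, in which case the log-rank p-value would be too small.

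**Working it through.** **The plan's own figures.** The documents give no power, effect size, event count or significance level for any biomarker test, so there is nothing to reproduce on this point. The neighbouring design figure in 13.6 (at least 10 of 24, 26% against 52%) does reproduce: exact power is 88.8% (stated as at least 88%) and exact one-sided error is 6.9% (limit 0.1).

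**Inputs from the documents.** 24 evaluable patients, 26 accrued in 24 to 28 months at about one a month, total duration 36 months (13.3); PFS at 6 months of 52% under the alternative (13.6).

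**Inputs assumed.** Exponential PFS; accrual uniform over 26 months; analysis at month 36; a normal marker measured in all 24 patients; a log-linear effect with hazard ratio 1.3 to 3.0 per SD; two-sided 0.05. The hazard at the mean marker value is −ln(0.52)/6 = 0.109 per month, which gives about 20 PFS events.

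**Approximate formula.** For D events and log hazard ratio b per SD, power is about Φ(√D·b − 1.96) with the continuous marker and Φ(√(2D/π)·b − 1.96) with a median split. With D = 20 and a hazard ratio of 2.0 (b = 0.693):

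- continuous: Φ(4.472 × 0.693 − 1.96) = Φ(1.14) = 87%
- median split: Φ(3.568 × 0.693 − 1.96) = Φ(0.51) = 70%

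The loss is 18 points before rounding. The formula is optimistic in a sample this small, so the simulated values below are preferred.

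**Simulation.** 4,000 trials per setting; Cox score test on the continuous marker against log-rank on a median split. The simulation error of one power figure is at most √(0.25/4000) = 0.8 points.

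| Hazard ratio per SD | Cox, continuous | Log-rank, median split | Loss (points) |
|---|---|---|---|
| 1.3 | 21% | 16% | 5 |
| 1.5 | 40% | 28% | 12 |
| 1.75 | 61% | 43% | 18 |
| 2.0 | 78% | 56% | 22 |
| 2.5 | 91% | 73% | 18 |
| 3.0 | 97% | 85% | 12 |

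Entering ranks instead of raw values keeps most of the gain (75% against 56% at a hazard ratio of 2.0). At two-sided 0.10, the loss over hazard ratios of 1.5 to 2.5 is 12 to 17 points.

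**Sensitivity.** With 40% progression-free at 6 months and three censoring patterns (about 15 to 24 events), the losses at 0.05 are 4 to 6 points at 1.3, 10 to 13 at 1.5, 17 to 19 at 1.75, 20 to 22 at 2.0, 15 to 21 at 2.5 and 11 to 18 at 3.0. The formula over 12 to 24 events goes down to about 0 at 3.0, where both tests are close to certain to reject.

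**Threshold effect at the median.** Same design, hazard ratio high against low, Cox on the raw marker against median-split log-rank:

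- hazard ratio 2: 21% against 24%
- hazard ratio 3: 45% against 51%
- hazard ratio 4: 60% against 66%

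Here the split is better by 3 to 6 points. Against rank-scored Cox its advantage is 0 to 1.5 points.

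**Open cut.** With no true association, the rejection rate at nominal 5% is 5.6% for Cox and 6.1% for the median split. Taking the largest log-rank statistic over all cuts that leave at least 6 patients on each side gives about 26% (41% to 42% at nominal 10%). Over a wider range, from the 20th to the 80th percentile, it is 30% to 33%.

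**The case against.** The strongest reply is that these analyses are exploratory. Section 13.8 describes them as mainly descriptive, the log-rank test goes with a display, and no decision rule depends on it. Exploratory objective 1 and the hypothesis in 2.3 concern response, and for response the plan already has an uncut Wilcoxon test. This stands, and it limits the weight of the point. It does not remove it: 13.8 still commits to the log-rank comparison and leaves its strata undefined.

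A second reply is that the simulated loss comes from a data model that favours Cox. That is fair. The marker distribution, the log-linear form and the effect size are assumptions, and a threshold at the median reverses the comparison. Section 9.3.2 also measures PD-L1 from whatever archival tissue remains, so fewer than 24 patients may have a value.

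Three stronger readings are tempting and are not supported:

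- That every biomarker in the trial is tested against PFS and OS only after cutting. Section 9.3.5.3 plans a Cox model for baseline MRI parameters, and 13.8 counts imaging among its biomarkers.
- That the investigators intend to search for the best cut. Nothing in 13.8 says so; the 26% shows what an open cut would allow.
- That the absence of a cited guideline for the log-rank comparison is a defect. An exploratory test needs none.

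**Conclusion.** The point holds for blood and tissue markers, as a minor improvement. Their only planned test against PFS and OS needs strata that the plan does not define, while a method that avoids the cut is already in the protocol for MRI parameters.

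The size is conditional. Under a log-linear effect of a normal marker, with 24 patients and about 20 PFS events, a median split costs about 5 points of power at a hazard ratio of 1.3 per SD, 12 to 22 at 1.5 to 2.5 and 12 at 3.0. A reader might take a loss of 10 to 20 points as a property of the trial; it is not, because the documents give no marker effect and a threshold at the median turns the loss into a small gain. The figures are for PFS. OS was not simulated, and they should not be carried over to it. The primary rule and the secondary endpoints are unaffected.

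**What to change.** In 13.8, replace the log-rank sentence with wording along these lines:

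> For blood and tissue markers measured on a continuous scale, the association of the baseline level with PFS and with OS will be tested in a univariable Cox model (score test), as for the MRI parameters in 9.3.5.3. The marker will enter uncut, as ranks, for all such markers. The hazard ratio will be given for a stated step on that scale with a two-sided 90% confidence interval. Kaplan-Meier curves split at the median are for display only. Log-rank tests will be used only for markers that are categorical by nature.

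Ranks are one choice. What matters is that a single scale is fixed beforehand for all markers, since a rule to transform only if skewed would leave a new choice open after the data are seen.

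The change needs no further patients, assays or data. The downside is slightly lower power if the true effect is a threshold near the median: 0 to 1.5 points with ranks, 3 to 6 with raw values. The retained Kaplan-Meier display would still show such a pattern. The change does not deal with multiplicity across the many markers, which remains a reason to read the results as exploratory.
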